STUDY PROTOCOL FOR A PROSPECTIVE, MULTICENTRE, COHORT STUDY: Preeclampsia sequential screening using angiogenic factors during 1st trimester of pregnancy (CRISP STUDY)

Date: 18.02.2021

ABSTRACT

Introduction. Preeclampsia (PE) affects from 2 to 8% of pregnant women. Recent studies show that prevention is the best strategy to improve perinatal outcomes. Therefore, the development of new strategies for preeclampsia screening becomes essential in order to determine the individual risk for each patient, and thus, to identify those who would be candidates for receiving prophylactic treatment with low-dose aspirin from the first trimester of pregnancy. The aim of our study is to determine prospectively, during clinical practice, the predictive and preventive capacity of a model of preeclampsia sequential screening in the first trimester of pregnancy.

Methods and Analysis. This is a prospective, multicentre, cohort study, with the collaboration of *Hospital de la Santa Creu i Sant Pau* (Barcelona), *Hospital Universitario de Cruces* (Bilbao), *Hospital Son Llàtzer* (Mallorca) and *Hospital Clínico Universitario Lozano Blesa* (Zaragoza). Women with a singleton pregnancy attending to the 12-week ultrasound scan at one of the maternity hospitals participating in the study between March 1st 2021 and 30th October 2022 will be recruited. Patients who accept to participate in the study will be classified into three risk groups (low-risk, moderate-risk and high risk) based on medical history, Mean Arterial Pressure (MAP), Pregnancy-Associated Plasma Protein A (PAPP-A) and Uterine Artery Pulsatility Index (UTPI). Placental Growth Factor (PIGF) will only be determined in those patients classified as intermediate risk after this first step and then reclassified in high and low-risk patients depending on its values. The number of first-trimester scans performed by these hospitals is approximately 8200 patients annually. Due to PE prevalence in our environment is around 3% of the total population, a total of 246 cases of PE are to be expected. Therefore, based on similar previous experiences, we could assume that 80% of the patients will accept to participate in the study, meaning a total sample of 6560 pregnant women.

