For this reason, different multivariant models have been developed, similar to those which are already used in other pregnancy diseases. Until now, the best PE early detection rates are obtained using an approach of competitive risks at 11-13 weeks of pregnancy by means of a combination of maternal characteristics (age, parity, medical history as thrombophilia, kidney disease and chronic hypertension), maternal biophysical variables (Mean Arterial Pressure (MAP), Doppler of Uterine Arteries (UTPI)) and biochemical variables (PIGF) that predicts approximately a 90% of early-onset PE (<32 weeks) and 75% of late-onset PE (<37 weeks) with a 10% false-positive rate (21, 22). Moreover, other observational retrospective studies have

demonstrated that the incorporation of antiangiogenic biomarkers as sFlt-1 can increase the predictive ability of the screening of PE during the first trimester (23).

Unfortunately, developing an universal screening system including angiogenic and antiangiogenic markers (PlGF and sFlt-1) has a high economical cost, which is hardly affordable for many Healthcare systems. For that reason, different PE-screening systems have been created at a lower cost. Maternal characteristics, arterial pressure and Uterine Arteries Pulsatility Index combined with Pregnancy-Associated Plasma Protein A levels (PAPP-A) presents a detection rate of early-onset PE of 80.8%, and for late-onset PE of 39.6%, with a 10% false-positive rate. This strategy does not increase the economic cost significantly, because PAPP-A is already used in the screening of chromosome disorders routinely (24).

However, recent retrospective studies with large sample sizes (25, 26) suggest a two-step screening. According to these analyses, similar detection rates are achieved if applying low-economic cost strategies to the entire population (12), but selecting a small group of patients with intermediate or high risk to determine angiogenic markers in only this group, being 30% of all pregnant women. Until now, these analyses have been performed in retrospective cohorts submitted to universal screening, with a high risk of methodological biases.

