Considering the number of first-trimester ultrasounds that are conducted in the participant hospitals, we estimate that 8200 patients will be potential candidates to participate in the study. Due to PE prevalence in our environment is around 3% of the total population, which means that approximately 246 patients of our sample will develop PE and based on similar previous experiences we could assume that around 80% of the patients will consent to participate in the study, meaning a total sample of 6560 pregnant women.

Based on a pilot study previously performed, we estimate that a 30% of the patients (which means approximately 1968 pregnancies) will be classified as intermediate or high risk after the PE universal screening. This sample size assures enough statistic power and the possibility of extrapolating the results to the clinical practice.

DATA COLLECTION

All the data required to carry out this study, including those derived from sonographies and blood tests, will be collected during the normal pregnancy control, without further appointments. This is one of the most important aspects of this project: developing an efficient

screening of preeclampsia during the first trimester using the explorations and visits that are already included in the pregnancy control.

The data will be collected during normal pregnancy control as follows:

A blood test will be requested in all pregnant women in the first appointment of pregnancy control between 9 and 13 weeks, to determine risk of chromosomal disorders according to the national protocol (*Sociedad Española de Ginecología y Obstetricia, SEGO*). This blood sample will be collected preferentially between 11 and 13 weeks, and it will be used this same sample to analyze angiogenic factors without requiring new blood extractions.

In the first-trimester scan, the mean uterine arteries pulsatility index will be determined, as well as mean arterial pressure. In this visit, the patient will be asked about her medical history. We will offer the patients the inclusion to our study in that moment; those who agree to participate in the study will sign the informed consent.

In patients who do not agree to participate in the sequential screening study, will be classified according to the algorithm without angiogenic factors, in:

Low Risk: (Preeclampsia Risk $<1/250$)

High Risk: (Preeclampsia risk $> 1/250$)

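### The 246 expected preeclampsia cases belong to the 8,200 candidates before consent; at the stated 3%, the sample of 6,560 gives about 197, and no target supports the power statement

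*Combined protocol and SAP*

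**What the plan says.** The Sample Size section builds its numbers in one chain. It starts from the candidate pool: "we estimate that 8200 patients will be potential candidates to participate in the study". It applies a preeclampsia (PE) prevalence of about 3% and concludes that "approximately 246 patients of our sample will develop PE". It then assumes that about 80% will consent, "meaning a total sample of 6560 pregnant women". The next paragraph takes 30% as intermediate or high risk after the first step, "which means approximately 1968 pregnancies", and ends with the claim: "This sample size assures enough statistic power".

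Four other places bear on these figures:
- **Abstract, Methods and Analysis.** It gives the 8,200 a time unit: "The number of first-trimester scans performed by these hospitals is approximately 8200 patients annually". It expects 246 cases without assigning them to the consenting sample.
- **Eligibility Criteria.** Recruitment runs from 1 March 2021 to 30 October 2022, and non-acceptance is listed as an exclusion.
- **Data Collection.** Women who decline "will be classified according to the algorithm without angiogenic factors", with a single cut-off.
- **Statistical Analysis.** Data from eligible women will be analysed whether they participate or refuse.

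**The concern.** The case count is attributed to the sample, yet it is computed before the step that defines the sample. The primary objective is the predictive and preventive capacity of the sequential screen. The number of PE cases among women who actually receive that screen limits how precisely its predictive part can be estimated. A reader who takes the section at face value will credit the study with more informative cases than its own inputs give.

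The closing sentence on power adds to this. It reads as the conclusion of a calculation, but none is shown and the case number before it is on the wrong base.

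**Working it through.** **Inputs.** From Sample Size: 8,200 candidates, 3% prevalence, 80% consent, 30% at intermediate or high risk. From the Abstract: 8,200 is an annual count. From Eligibility Criteria: the recruitment dates.

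**Reproducing the plan's figures**
- PE cases: 0.03 × 8,200 = 246. This matches, on the pre-consent base.
- Participants: 0.80 × 8,200 = 6,560. This matches.
- Intermediate or high risk: 0.30 × 6,560 = 1,968. This matches, on the post-consent base (0.30 × 8,200 would be 2,460).

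**Cases on the stated sample**
- 0.03 × 6,560 = 196.8, about 197.
- Overstatement: 246 / 196.8 = 1.25, or 25%.
- Prevalence needed for 246 cases in 6,560 women: 246 / 6,560 = 3.75%, a value that the documents do not give.

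**Where the other cases are**
- Refusers: 0.20 × 8,200 = 1,640.
- Assuming 3% among them as well: 0.03 × 1,640 = 49.2, and 196.8 + 49.2 = 246.

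**Time base**
- 1 March 2021 to 30 October 2022 is 20 months.
- If 8,200 is annual, volume is constant and all scans are eligible (assumptions): 8,200 × 20/12 = 13,667 candidates.
- Participants: 0.80 × 13,667 = 10,933.
- PE cases among participants: 0.03 × 10,933 = 328. Among all candidates: 0.03 × 13,667 = 410.
- Intermediate or high risk: 0.30 × 10,933 = 3,280.
- These are upper figures, because some scans may be ineligible. On this reading too, participants do not yield 246 cases.

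**Effect on precision**
- The 95% half-width for a proportion p among n cases is 1.96 × √(p(1−p)/n). Going from 246 to 196.8 cases multiplies it by √1.25 = 1.118, about 12%, whatever p is.
- Illustration at an assumed p = 0.75 among all PE cases: 1.96 × √(0.75 × 0.25 / 246) = 5.4 points; with 197 cases it is 6.05 points.
- This interval is only a yardstick. Statistical Analysis plans the area under the ROC curve and a goodness-of-fit test, and no such interval.

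**Power.** No calculation can be run. The documents give a 0.05 significance level but no power, effect size, margin, precision or required number of cases.

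**The case against.** The best defence is that 246 describes everyone who will be analysed. It follows directly on the 8,200 candidates, before consent is applied; the Abstract's own use of it is right for 8,200 scans; and Statistical Analysis includes women who refuse. On that population 246 is correct, and the error is then one of labelling. Nothing else computed in the documents depends on the figure.

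Part of this stands: the number is sound for all candidates and the consequence is limited. It does not rescue the sentence. The same section calls 6,560 the total sample, Eligibility Criteria excludes women who do not accept, and refusers receive only the screen without angiogenic factors. Their cases can inform that screen but not the sequential one.

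Three stronger readings are tempting, and the documents do not support them.
- **The study is underpowered.** With no target stated, adequacy can be neither shown nor refuted.
- **The annual 8,200 against a 20-month window is a second proven error.** Sample Size gives no period and speaks of potential candidates, so the pool may be defined differently there. The two places need reconciling, no more.
- **The loss of precision is large, or can be tabulated for the detection rates in the Introduction.** Those rates are for subgroups, for example "for late-onset PE of 39.6%, with a 10% false-positive rate", and cannot be applied to all PE cases. Aspirin use and deliveries elsewhere could lower the observed count, but the documents give no figure from which to size that loss.

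**Conclusion.** The point holds. As written, the expected case number in the sample is wrong: about 197, not 246, a 25% overstatement for the women who inform the primary objective. This rests only on the section's own 3%, 80% and 8,200, with 8,200 taken as the full candidate pool. The split that puts about 49 cases among refusers assumes the same 3% in them. The figure of 328 for the full window assumes constant volume and full eligibility.

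The consequence is modest: intervals about 12% wider than 246 cases would suggest, before any losses. The power sentence has no stated basis, which is a gap in the justification and not evidence that the study is too small.

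**What to change.** In this order:

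1. State whether 8,200 is one year's volume or the candidate pool for the whole recruitment window, and whether ineligible women are already removed.
2. In both the Abstract and Sample Size, give participants, PE cases and risk-group counts on the same post-consent base. If 8,200 is the full pool, these are about 6,560, 197 and 1,968. If it is annual and volume is constant, they are up to about 10,930, 328 and 3,280.
3. Label 246 as the cases expected among all 8,200 candidates, refusers included.
4. Reconcile Eligibility Criteria with Statistical Analysis on whether refusers are analysed. If they are, say that they contribute only to the screen without angiogenic factors.
5. Delete the power sentence, or replace it with the expected precision, at the case number from step 2, of a measure that the analysis will report.

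These are changes of text and need no extra patients. The cost is that the stated case number becomes less favourable, falling from 246 to about 197, if 8,200 is the full pool.

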The aim of this study is to evaluate prospectively, for the first time and in a clinical scenario, a population sequential screening of preeclampsia, saving the determination of angiogenic factors (PlGF, sFlt-1) to a subgroup of patients with an intermediate risk after the first step of the screening, maintaining a high detection rate but with a lower economic cost.

National and international groups working on preeclampsia

Preeclampsia is one of the most important research topics in maternal-fetal medicine, being the screening of this disease the most important point of interest due to its high clinical impact. [name] (PI of Hospital de la Santa Creu I Sant Pau research group) is an international leader in preeclampsia. All the Hospitals participating in this study have worked, in the last years, on different projects focused on preeclampsia and placental insufficiency, some of them collaborating between them (PI16/00375) (MSC EC10-205). Besides, these investigation groups share research lines with the most important international groups working on PE at this moment: Kings College (London), Oxford University, Johns Hopkins University and Charité University Medicine (Berlin).

HYPOTHESIS

Primary hypothesis

It is possible to perform a sequential population screening of PE, saving the determination of angiogenic markers (PIGF+/- sFlt-1) for the subgroup of patients with an intermediate risk of having PE, maintaining a high rate of detection of PE but with a lower economic cost.

Secondary hypothesis

sFlt-1 measurement increases the PE detection rate during the first trimester of pregnancy if determined at subgroups at risk.

Universal PE screening during the first trimester without angiogenic factors (medical history + MAP + UTPI + PAPP-A) selects effectively those patients with a high or intermediate risk of having PE without increasing the cost of the assistance. Sequential population screening of PE presents a similar detection rate of IUGR but with a lower economic cost.

OBJECTIVES

Primary objectives

To determine prospectively, in a clinical scenario, the predictive and preventive capacity of a sequential screening of PE in the first trimester of pregnancy; determining Placental Growth Factor (PIGF) only in those patients classified as intermediate risk after the universal screening without angiogenic factors: medical history, Mean Arterial Pressure (MAP), Pregnancy-Associated Plasma Protein-A (PAPP-A), Uterine Artery Pulsatility Index (UTPI).

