In the participants, the initial risk of PE will be calculated using maternal medical history, MAP, UTPI and PAPP-A (already used in aneuploidies screening), using the software validated to each laboratory. Patients will be classified into 3 groups:

- Low risk of PE ($<1/500$)
- Intermediate risk of PE (between $1/50$ and $1/500$)
- High risk of PE ($>1/50$)

In those patients classified as intermediate and high-risk, PIGF and s-Flt-1 will be determined from the blood samples kept in biobanks of each hospital according to the current legislation. sFlt-1 results will be analyzed at the end of the study in order to decrease the cost because there will not be used to make clinical decisions. PIGF in high-risk patients will not be considered either to reclassify those patients. In both cases, the diagnostic efficiency will be analyzed at the end of the study.

Patients in the intermediate-risk group (1/50-1/500) will be reclassified after adding PIGF levels in the predictive algorithm in 2 groups: Low risk of PE (<1/160) and High risk of PE (>1/160).

To the patients classified as high risk at any of the steps, will be offered prophylactic treatment with Acetylsalicylic acid (ASA) (150mg/24h) until 36 weeks of pregnancy, if there is not a contraindication.

The cut-off point of high risk after combined PE screening without using angiogenic factors had been obtained from a pilot study performed in *Hospital de la Santa Creu i Sant Pau* and *Hospital Universitario de Cruces*. According to this initial estimate with the selected cut-off point we expect to find 10% of high-risk patients and 20% of intermediate-risk after the first step of the screening. These results are in agreement with those published by other authors (25).

STATISTICAL ANALYSIS

All data from eligible patients, both those who participate in the study and those who reject it and therefore a one-step screening will be performed, will be analyzed.

The entire research team will participate in the recruitment and every team member will be responsible for the data that will be included in the electronic database, predictive variable and outcomes. This database will be anonymous and codified.

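### The claim that sequential screening maintains PE detection has no planned comparison behind it; a paired comparison with one-step screening in participants needs no new data and should be specified

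*Combined protocol and SAP*

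**What the plan says.** **Claim.** The Hypothesis section proposes sequential screening "maintaining a high rate of detection of PE but with a lower economic cost". A secondary hypothesis is also comparative: "Sequential population screening of PE presents a similar detection rate of IUGR but with a lower economic cost". Neither names a reference strategy, a margin or a fixed FPR.

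**Who is measured.** Data Collection: "In those patients classified as intermediate and high-risk, PIGF and s-Flt-1 will be determined". Women below 1/500 at step 1 get no PlGF. In the same section, "we expect to find 10% of high-risk patients and 20% of intermediate-risk after the first step of the screening", which leaves about 70% low risk. Intermediate women are reclassified at 1/160 after PlGF. High-risk women are not reclassified. Women who are high risk at either step are offered aspirin.

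**Refusers.** They "will be classified according to the algorithm without angiogenic factors", with a single cut-off of 1/250. The Statistical Analysis section includes them: "both those who participate in the study and those who reject it and therefore a one-step screening will be performed". The Eligibility Criteria list non-acceptance as an exclusion.

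**Background rates.** The Introduction gives, for the model with PlGF, about 90% of PE before 32 weeks and "75% of late-onset PE (<37 weeks) with a 10% false-positive rate". For the PAPP-A model without PlGF it gives 80.8% (early) and 39.6% (late), also at 10% FPR. The primary outcome is any PE.

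**Planned analysis.** Bivariate tests, logistic regression, the Hosmer-Lemeshow test and the area under the ROC curve of a final model. A secondary objective covers the diagnostic and economic yield of screening without angiogenic factors.

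**The concern.** To say that detection is maintained is to compare it with something. None of the listed analyses scores the fixed 1/50, 1/500, 1/160 rule, and none compares it with another strategy. The AUC of a newly fitted logistic model describes that model, not the classification used to offer aspirin.

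Without a stated comparison, the report will have to fall back on whatever is to hand, and each option is unlike. Universal PlGF screening cannot be reconstructed in the low-risk group. A participant-refuser contrast mixes the strategy, the cut-off and who consents, and it rests on few refuser cases. The background rates differ in FPR and in outcome definition. A rule that flags more women can appear to hold its detection rate through its cut-off alone, with no contribution from PlGF.

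**Working it through.** **1. The plan's own figures (Sample Size).** 8200 × 0.80 = 6560; 8200 × 0.03 = 246; 6560 × 0.30 = 1968. All reproduce. The 246 cases belong to all 8200 eligible women, however. Participants give 6560 × 0.03 ≈ 197 cases and the 1640 refusers give 1640 × 0.03 ≈ 49. If 8200 is annual, as the Abstract says, 20 months give 8200 × 20/12 ≈ 13,667 women, with 328 and 82 cases.

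**2. FPR of the sequential rule.** The screen-positive rate is S = 10% + f × 20%, where f is the share of intermediates that become high risk. The documents do not give f. Assuming 10–40%, S = 12–18%. With detection D and 3% prevalence, FPR = (S − 0.03D)/0.97.

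- S = 12%, D = 75%: (0.12 − 0.0225)/0.97 = 10.05%.
- FPR is exactly 10% at D = 75% when S = 0.097 + 0.0225 = 11.95%, that is f = 9.75%.

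To isolate the effect of the cut-off, assume a binormal ROC curve, D = Φ(d + z(FPR)), and solve it jointly with the FPR formula.

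| Background rate at 10% FPR | d | S = 12% | S = 18% |
|---|---|---|---|
| 75% | 0.674 + 1.282 = 1.956 | FPR 10.05%, D 75.1% | FPR 16.0%, D 83.2% |
| 39.6% | −0.264 + 1.282 = 1.018 | FPR 11.1%, D 41.9% | FPR 16.9%, D 52.4% |

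The cut-off alone therefore moves 75% to 75–83% and 39.6% to 42–52%.

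**3. Precision (95% half-width, assumed 70% detection and 15% discordance among cases).**

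- Participants against refusers: 1.96 × √[0.21 × (1/197 + 1/49)] = 14.3 points (11.1 with 328 and 82 cases).
- Paired in participants: 1.96 × √(0.15/197) = 5.4 points (4.2 with 328 cases).

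Power for an assumed 10-point non-inferiority margin, Φ(0.10/SE − 1.96), is 25–55% unpaired over detection of 60–90%, and 99/88/73% paired at 10/20/30% discordance. For a 5-point margin the paired power is 60/35/25%.

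**4. Where the two rules can differ.** Since 1/250 lies between 1/500 and 1/50, step-1 high-risk women are positive on both rules and step-1 low-risk women negative on both. All discordance falls among intermediates, where PlGF acts. The two rules still need not flag the same share. A lognormal risk distribution fitted to 10% above 1/50 and 30% above 1/500 (an assumption) puts 22.6% above 1/250, against 12–18% for the sequential rule. A matched threshold is needed alongside 1/250. Matching at a fixed 10% is uninformative: step-1 high risk alone is expected to reach 10%, so the sequential rule would reduce to step 1.

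**5. Aspirin.** Let both rules truly detect 75%, with discordance q split equally. Suppose aspirin prevents a share e of cases in sequential-positive women only. The observed paired difference is −(q/2)e/(1 − 0.75e).

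- q = 10%, e = 20%: −0.05 × 0.20/0.85 = −1.2 points.
- q = 15%, e = 62%: −0.075 × 0.62/0.535 = −8.7 points.
- q = 30%, e = 62%: −0.15 × 0.62/0.535 = −17.4 points.

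The 62% is the Introduction's figure for preterm PE, used here only as an upper end.

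**6. Bound for universal PlGF.** With the same PlGF algorithm and the 1/160 cut-off applied to everyone, intermediates are classified as now and step-1 high-risk women can only be lost. Any gain must come from step-1 low-risk women, so their share of PE cases caps it. Cases prevented by aspirin in the other groups raise the observed share, so it remains an upper bound.

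**The case against.** The strongest reply is that the primary objective is to estimate predictive and preventive capacity, and that maintaining a high rate can be read as an absolute statement. The background rates are not declared as test benchmarks, and the plan says refusers' data will be analysed, not that their detection rate will be contrasted with participants'. All of that is correct. A reader might infer that the protocol plans a faulty test against refusers or published rates; it does not. What stands is that no comparison is planned at all. Read as absolute, the claim has no threshold, and the listed analyses still give no detection rate.

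It can also be said that the secondary objective on screening without angiogenic factors already covers the one-step rule. It does make one-step performance an aim, but it plans no comparison within the same women.

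Two objections limit the remedy. Saving angiogenic assays while maintaining detection most naturally points to universal angiogenic screening, and the paired analysis does not answer that. And because aspirin follows the sequential result, an unadjusted McNemar test is biased; at 15% discordance and a 62% effect the bias (8.7 points) exceeds the half-width (5.4). Both stand, and they set the limits of the fix.

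Finally, a reader might take 12–18% positive as the FPR and infer that detection is always inflated. At 3% prevalence, 12% positive is about 10% FPR, so at that end the 75% figure does not move.

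**Conclusion.** The concern holds in this form: the analyses listed cannot test whether detection is maintained, and a better comparison is available from data the study already collects. Pairing cuts the half-width from about 14 to about 5 points before aspirin bias, at an assumed 70% detection and 15% discordance. Cut-off alone could add 0–8 points to the 75% rate and 2–13 points to the 39.6% rate, if 10–40% of intermediates become high risk and the ROC curve is binormal. Aspirin bias runs from about −1 to −17 points for 10–30% discordance and a 20–62% effect, assuming equal true detection of 75% and aspirin confined to sequential-positive women.

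A reader might infer that a favourable paired result would show detection maintained against universal PlGF. It would not, since low-risk women have no PlGF; the documents support a claim only against one-step screening without PlGF, plus the bound. The paired analysis should be specified; the study does not otherwise need redesign.

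**What to change.** In the Statistical Analysis section, specify the following for participants.

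- Score the one-step rule from the step-1 risk already calculated for every woman.
- Report detection rate and FPR of both rules with 95% CIs, and the paired differences (McNemar among PE cases and, separately, among non-cases).
- Do this with the one-step rule at 1/250 and at the threshold that gives the screen-positive rate the sequential rule actually shows. The matched threshold is for analysis only and should not be fixed at 10%.
- Prespecify a sensitivity analysis for aspirin over a stated range of effects and state the direction of the bias, which is against the sequential rule.
- Limit the maintained-detection claim to one-step screening without PlGF, and report the share of PE in step-1 low-risk women as the upper bound on what universal PlGF could add.
- Reconcile the Eligibility Criteria, which exclude refusers, with the Statistical Analysis section, which includes them.

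The cost is SAP wording, one more analysis and a narrower claim. No new assay, visit or data item is needed, and no clinical cut-off changes.
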